## 5.5 Study Evaluations Veteran Assessment

Primary Outcome: Veteran Community Integration. Our original measure, the Sydney Psychosocial Reintegration Scale (Tate et al., 2011), normed for non-military TBI survivors in Australia, will be supplemented by the computer adaptive test version of the Community Reintegration of Injured Service Members (CRIS-CAT) (Resnik et al., 2012), developed and normed specifically for the OEF/OIF cohort. Due to a recently developed computer adaptive format, the CRIS-CAT is now a feasible measure, requiring only 10 minutes to complete.

Secondary Outcome: Veteran Emotion Regulation and Interpersonal Skills. Two measures will be used to assess change in the Veteran's use of adaptive social behaviors needed for community reintegration. Emotion regulation, currently assessed by the AX scale of the State-Trait Anger Expression Inventory (Spielberger & Sydeman, 1994), will be evaluated more directly by the Difficulties in Emotion Regulation Scale (DERS) (Gratz & Roemer, 2004), which is comprised of six orthogonal factors (nonacceptance, goals, impulse, awareness, strategies, and clarity), that together explain 56% of the variance in emotion regulation and has a Cronbach's alpha = .85 (Gratz & Roemer, 2004). In addition, the Abbreviated Duke Social Support Scale (ADSSI) (Koenig et al., 1993) will be used to measure both subjective support and social network interactions. To measure social interaction, Veterans are asked to describe their telephone and face-to-face interaction patterns and attendance at clubs and religious events during the past week outside of work. To measure subjective support, they are asked to respond to questions such as "Does it seem that your family and friends understand you most of the time, some of the time, or hardly ever?"

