missing data points and unequal intervals between testing occasions. Choices of variancecovariance structures to account for within-subject correlation will be made based on the AIC, BIC, or likelihood ratio statistic. All principal analyses will be conducted based on the intentionto-treat principle in which any participant randomized to a treatment arm remains in it regardless of adherence to or completion of treatment. We will measure the level of participation, and will conduct a sensitivity analysis that assesses the stability of the conclusions from this study with an intention-to-treat analysis versus an analysis that takes into account level of adherence. With multiple time points and variables representing outcomes at both the individual and couples level, the planned analyses involve multiple comparisons raise concerns about the increased likelihood that any single outcome will be found to be statistically significant based on chance alone. In order to minimize this risk, we have carefully selected a limited number of outcomes and clearly designated primary, secondary and exploratory outcomes. Our primary outcomes for the Veteran and for the caregiver are each represented by a single measure. For models evaluating the effect of treatment assignment on constructs represented by more than one measure, e.g., Veteran Emotion Regulation and Interpersonal Skills, we will employ Bonferroni's correction to adjust each observed p-value by the number of tests performed and have calculated power on this basis (see power calculations below).

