### Tests of Specific Study Hypotheses:

### **Primary Hypotheses:**

Hypothesis 1: Veterans with mTBI treated with 6 months of multi-family group for couples (MFG-mTBI-C) will show improved community integration (primary outcome), and improved anger management and use of social support (secondary outcomes) compared with those treated in a health education group without training in communication skills or compensatory strategies; Changes in the primary study outcomes (Sydney Psychosocial Reintegration Scale) from baseline for each treatment group at each time point will be examined using paired t-tests or Wilcoxon signed-rank tests as appropriate. Differences in changes in mean Sydney scores from baseline between two treatment groups will be compared using t-tests or Wilcoxon rank-sum tests as appropriate at each time point. Linear mixed models will be used to examine changes in scales over time and to examine whether the effects of MFG-mTBI-C on the Sydney and secondary Veteran outcomes (DERS and social support scales) vary with time and study sites adjusted for the time-dependent treatment, imbalanced baseline prognostic factors (if applicable), and control variables relating to combat/ injury exposure (mechanism of injury (blast vs. other), # deployments, # TBI's and degree of exposure to war zone violence/threats). In addition, Spearman correlation coefficients will be used to assess associations of changes in the Sydney with changes in Veteran symptoms from baseline at each time point and to examine whether degree of associations increases over time among Veterans treated with MFG-mTBI-C. If significant patterns over time are observed in any of these variables, mixed models will then be used to examine the effects of the variables identified on CI change over 6 months post treatment.

Hypothesis 2: Caregivers whose Veteran spouse/partners are treated with MFG-mTBI-C will show reduced burden (primary caregiver outcome) over the course of treatment and in the 6-month follow-up period relative to caregivers whose Veteran partners are treated in a health education group. The analytic plan proposed in Hypothesis 1 will be used for assessing effects of MFG-mTBI-C on changes in the CBI.

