Secondary Outcomes: We calculated power for the Veteran secondary outcomes, AX (anger expression) and Duke (social support) scales for a two-sided, two-sample t-test, using the same assumptions for calculating primary outcomes and the observed correlation coefficients of .90 and .72, respectively for a two sample t-test, with alpha=0.025. Based on these assumptions, we have 94% power to detect an effect of .5 on the AX scale and 81% power to detect an effect of .5 on the Duke scale. Covariates: Due to the high degree of comorbidity in this cohort of Veterans, we have specified a number of variables for potential inclusion as covariates in our analytic models, should randomization result in an imbalance. These include Veteran (and where appropriate caregiver) physical health, substance use, service use (including starting and stopping treatment), level of depressive and post-traumatic stress symptoms, as well as usual sociodemographic (race/ethnicity, gender, age, SES) and military (e.g., number of deployments) variables. As noted above under General Approach, we will employ t-tests or Wilcoxon ranksum for continuous variables, and chi-square or Fisher's exact tests for categorical variables at baseline to identify any imbalance between groups on these variables, and will control for any imbalance by including variables that differentiate groups at conventional levels by including them in our analyses as covariates. However, as discussed, given random assignment of a sample of 180 to one of two treatment groups, we anticipate that few if any variables will differentiate between groups, and that our power analyses are conservative enough to accommodate inclusion of a limited number of covariates if necessary. Potential inclusion of covariates as "control variables" should be distinguished from inclusion of covariates for the purpose of testing exploratory mediating/moderating hypotheses as described under hypotheses 3 and 4 above.

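### Plain Bonferroni for the two-measure secondary construct gives up power for nothing: Holm's procedure would lift Duke power from the stated 81% to about 87% at the same 5% family-wise level

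*Combined protocol and SAP*

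**What the plan says.** Section 5.6, General Approach, names several time points and several variables as sources of multiplicity. Its first remedy is a limited set of outcomes sorted into primary, secondary and exploratory. For constructs with more than one measure it adds: "we will employ Bonferroni's correction to adjust each observed p-value by the number of tests performed and have calculated power on this basis". Its example is Veteran Emotion Regulation and Interpersonal Skills.

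Section 5.5 gives that construct two measures. One is the DERS, which takes over from the AX anger scale. The other is the abbreviated Duke scale (ADSSI), which "will be used to measure both subjective support and social network interactions".

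Hypothesis 1 in section 5.6 assigns these outcomes to linear mixed models that ask whether "the effects of MFG-mTBI-C on the Sydney and secondary Veteran outcomes (DERS and social support scales) vary with time and study sites".

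The Secondary Outcomes paragraph of the power calculation reads: "We calculated power for the Veteran secondary outcomes, AX (anger expression) and Duke (social support) scales for a two-sided, two-sample t-test". Its inputs are pilot correlations of .90 for AX and .72 for Duke, and its level is given as "for a two sample t-test, with alpha=0.025". Its conclusion, in which the 81% belongs to Duke, is: "we have 94% power to detect an effect of .5 on the AX scale and 81% power to detect an effect of .5 on". Elsewhere in section 5.6 a randomised sample of 180 is cited, and Tables 8 and 9 start from 90 per cell. Section 5.1 and Table 4 plan 150, or 75 per arm.

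**The concern.** Bonferroni tests both measures at 0.025 whatever the other one shows. With two tests this is stricter than 5% control requires. Once one null hypothesis has been rejected at 0.025, the other can be tested at 0.05 without raising the family-wise rate.

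Suppose the DERS gives p = 0.01 and the Duke gives p = 0.04. Under the planned rule the Duke p-value is doubled to 0.08 and the result is not significant. Under Holm the smaller p-value is doubled to 0.02 and the larger stays at 0.04, so both are significant.

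The weaker-powered measure loses most. The Duke starts at 81% on the plan's own figures, and lower at the sample size now planned. A real effect on social support could be missed because of a correction that protects no better than its alternative.

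**Working it through.** **Inputs.** From the Secondary Outcomes power paragraph: two-sided alpha 0.025, Duke power 81%, AX power 94%. From section 5.5: two measures. From Tables 8 and 9 and Table 4: 90 and 75 per arm.

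**1. The plan's alpha.** 0.05/2 = 0.025 exactly. The rule and the power statement agree when tests are counted by measure.

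**2. The plan's powers.** These cannot be reproduced, because the Duke and AX mean changes, their standard deviations and the attrition used are not given.
- A standardised difference of 0.50 at alpha 0.025 gives 86.7% at n = 90 per arm, 80.0% at 76, 77.6% at 72 and 74.3% at 67. Only n = 76 comes near 81%, and the same inputs cannot also give 94% for AX.
- Converting through the pilot correlation, 0.5/√(2(1−ρ)), gives 95-99% for the Duke, which does not fit either.

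The stated powers are therefore taken as given.

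**3. Back-solved noncentrality** (normal approximation): δ = z(0.9875) + z(power), with z(0.9875) = 2.241.
- Duke: 2.241 + 0.878 = 3.119
- AX: 2.241 + 1.555 = 3.796

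**4. Power at an unadjusted 0.05:** Φ(δ − 1.960).
- Duke: Φ(1.159) = 87.7%
- AX: Φ(1.836) = 96.7%

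**5. Holm with two tests.** A measure is declared significant if its own p ≤ 0.025, or if its p lies between 0.025 and 0.05 and the other measure has p ≤ 0.025. With independent tests:
- Duke: 81.0 + (87.7 − 81.0) × 0.94 = 87.3%
- AX: 94.0 + (96.7 − 94.0) × 0.81 = 96.2%

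Simulation at between-test correlation 0.5 gives 86.9% and 95.4%.

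**6. Error control.** If both nulls are true, the first rejection needs a p-value at or below 0.025, so the family-wise rate is at most 2 × 0.025 = 5%. If only one null is true, it can be rejected only at p ≤ 0.05. The 5% limit holds in both cases.

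**7. At the planned size.** At equal attrition the noncentrality scales by √(75/90) = 0.913.
- Duke: δ = 2.847. Bonferroni Φ(0.606) = 72.8%; unadjusted Φ(0.887) = 81.3%.
- AX: δ = 3.465. Bonferroni Φ(1.224) = 89.0%.
- Duke under Holm, independent tests: 72.8 + (81.3 − 72.8) × 0.89 = 80.4%. Simulation at correlation 0.5 gives about 80%.

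**8. If only the Duke effect is real.** The other test then passes 0.025 with probability 0.025, and Holm gives 81.0 + 6.7 × 0.025 = 81.2%. Almost nothing is gained, and nothing is lost.

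**The case against.** The strongest reply is that Bonferroni is valid, was specified in advance and was used for the power, so preferring Holm is a matter of taste. The first part stands: nothing is wrong with the error control, and this is not a flaw in the plan. The second part does not stand, because Holm gives the same guarantee and rejects everything Bonferroni rejects. The gain does depend on both effects being real. If only one is, Holm is practically the same as Bonferroni.

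A reader might go further and infer that the planned analysis contains three, four or six secondary tests, so that 0.025 is the wrong level. Those counts need either separate tests of the two ADSSI components or separate tests at each post-baseline visit. The documents specify neither. Section 5.5 describes two measures, Table 5 has a single Veteran row for the Duke scale, and group comparisons at each time point are written out only for the Sydney. A mixed model can supply one treatment contrast per measure.

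A reader might also infer that family-wise error exceeds 5%. The rule adjusts each p-value by the tests actually performed, and 0.025 appears only in the power statement, not as a decision threshold. Extra tests would cost power, not error control.

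**Conclusion.** This is a free improvement, not an error. On the plan's own stated powers, Holm raises Duke power from 81% to about 87% and AX power from 94% to about 95-96%, with family-wise error still at or below 5%. These figures rest on the normal approximation, both effects being real, and a between-test correlation of 0 to 0.5.

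The documents do not support saying that the 81% is lost because there are more than two tests. They do leave the score and time point of each secondary contrast, and hence the divisor, unstated. That is missing detail worth settling in the same edit.

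The stated powers need updating for a different reason. They come from a power section that assumes 180 participants rather than 150. At 75 per arm and the same attrition, Duke power is about 73% under Bonferroni and about 80% under Holm. The 94% belongs to AX, and the documents give no figures from which to derive the power for the DERS.

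**What to change.** In section 5.6, General Approach, replace Bonferroni's correction with Holm's step-down procedure at a two-sided family level of 0.05. Apply it to exactly two tests: one treatment contrast from the mixed model, at one named time point, for the DERS total score, and the same contrast for the ADSSI total score. Label other visits, subscores, and treatment-by-time and treatment-by-site tests of these outcomes as exploratory.

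In the Secondary Outcomes paragraph, restate power for 75 per arm with the attrition assumption shown, and for the DERS in place of AX. Where no DERS pilot figures exist, state the assumption and give a range.

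The cost is wording plus one power recalculation. Data collection and sample size do not change. The restated power will probably look less favourable than 81% and 94%, and the remaining visits and subscores will have no confirmatory status.

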### Tests of Specific Study Hypotheses:

### **Primary Hypotheses:**

Hypothesis 1: Veterans with mTBI treated with 6 months of multi-family group for couples (MFG-mTBI-C) will show improved community integration (primary outcome), and improved anger management and use of social support (secondary outcomes) compared with those treated in a health education group without training in communication skills or compensatory strategies; Changes in the primary study outcomes (Sydney Psychosocial Reintegration Scale) from baseline for each treatment group at each time point will be examined using paired t-tests or Wilcoxon signed-rank tests as appropriate. Differences in changes in mean Sydney scores from baseline between two treatment groups will be compared using t-tests or Wilcoxon rank-sum tests as appropriate at each time point. Linear mixed models will be used to examine changes in scales over time and to examine whether the effects of MFG-mTBI-C on the Sydney and secondary Veteran outcomes (DERS and social support scales) vary with time and study sites adjusted for the time-dependent treatment, imbalanced baseline prognostic factors (if applicable), and control variables relating to combat/ injury exposure (mechanism of injury (blast vs. other), # deployments, # TBI's and degree of exposure to war zone violence/threats). In addition, Spearman correlation coefficients will be used to assess associations of changes in the Sydney with changes in Veteran symptoms from baseline at each time point and to examine whether degree of associations increases over time among Veterans treated with MFG-mTBI-C. If significant patterns over time are observed in any of these variables, mixed models will then be used to examine the effects of the variables identified on CI change over 6 months post treatment.

Hypothesis 2: Caregivers whose Veteran spouse/partners are treated with MFG-mTBI-C will show reduced burden (primary caregiver outcome) over the course of treatment and in the 6-month follow-up period relative to caregivers whose Veteran partners are treated in a health education group. The analytic plan proposed in Hypothesis 1 will be used for assessing effects of MFG-mTBI-C on changes in the CBI.

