#### General Approach:

Preliminary analyses including computing descriptive statistics and inspecting features and patterns of data to determine whether data transformations are necessary will be performed. We will test whether clinical characteristics of the study population, (e.g., age, sex, race, PTSD comorbidity), and other variables known to be prognostically related to the primary outcomes, are comparable between two treatment groups at baseline, using t-tests or Wilcoxon rank-sum for continuous variables, and chi-square or Fisher's exact tests for categorical variables. Groups will be considered imbalanced on variables that differ between them at p < .10 and all such imbalanced baseline prognostic factors will be included in primary analyses as control variables. Psychometric analyses will be conducted to check the properties of the scales for this sample. Outcome variables such as the Sydney and CBI will be measured at three time points for each participant. Because repeated measurements on individual subjects tend to be correlated and in some cases, the number and spacing of observations may vary among subjects, we will examine these data by graphic displays of outcome variables versus time and individual subject and mean profiles to assess the mean structure for modeling fixed effects and to examine whether there are heteroscedasticity and/or curvature in the data. Linear mixed models (LMM), generalized linear mixed models (GLMM) or generalized estimating equations (GEE) will then be used to account for dependence of repeated measures and to accommodate correlated errors, unequal correlations among time points, unbalanced data resulting from

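### For the Sydney and the CBI, the plan names no decisive contrast or time point and does not say how the baseline score enters the mixed model

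*Combined protocol and SAP*

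**What the plan says.** **Model class.** The Abstract and the Overview in section 5.1 both plan an intention-to-treat comparison of the arms by mixed effects regression. Neither names a model term, contrast or visit.

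**Tests for the Sydney (section 5.6, Hypothesis 1).** The plan states "Differences in changes in mean Sydney scores from baseline between two treatment groups will be compared using t-tests or Wilcoxon rank-sum tests", and continues "as appropriate at each time point. Linear mixed models will be used to examine changes in scales over time". Three measurements are planned, so the between-arm change tests fall at two time points: post-treatment and 6 months. The mixed model is "adjusted for the time-dependent treatment, imbalanced baseline prognostic factors (if applicable), and control variables relating to" combat and injury exposure. The baseline Sydney score is not among the listed adjusters.

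**Tests for the CBI (Hypothesis 2).** The analysis is that of Hypothesis 1. The hypothesis is that caregivers "will show reduced burden (primary caregiver outcome) over the course of treatment and in the 6-month follow-up period".

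**General Approach.** It notes that "Outcome variables such as the Sydney and CBI will be measured at three time points for each participant", and that "Linear mixed models (LMM), generalized linear mixed models (GLMM) or generalized estimating equations (GEE) will then be used" to handle the repeated measures. On multiplicity it says "With multiple time points and variables representing outcomes at both the individual and couples level, the planned analyses involve multiple comparisons". Its answer is a limited set of ranked outcomes, a single measure for each primary outcome, and a Bonferroni correction. The correction applies as follows: "For models evaluating the effect of treatment assignment on constructs represented by more than one measure".

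**Covariates.** General Approach adds prognostic factors that differ between arms at p < .10. The Covariates paragraph (after the power calculation) refers back to General Approach but sets the threshold at the conventional level, with no number.

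**The concern.** A primary outcome needs one test that decides it. Here the Sydney and the CBI each have two follow-up time points, a parametric and a rank version of the change test, and a mixed model, with no order among them. The plan recognises multiple time points as a source of chance findings, but its one formal correction covers constructs with several measures. A primary outcome with one measure and two time points falls outside it. If a favourable result at either visit may be reported as success, the 5% level is not kept.

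The second gap concerns precision. A change score subtracts the baseline in full, whereas regression on baseline gives it the weight that the data support. A three-visit mixed model can match either one. If arm means are left free at baseline, its contrast is the change-score contrast. If arms are held equal at baseline, it does about as well as using baseline as a covariate. The plan does not say which model it means, so the choice could be made after data are seen.

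Third, choosing covariates by baseline significance tests makes the primary model depend on chance imbalance and not on prognostic value, and the two wordings of the threshold could give different models.

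**Working it through.** **1. The plan's own power figures.** Inputs: Tables 8 and 9, effect .5, two-sided alpha .05, planning correlation .5, and 76, 72 or 67 per arm after attrition. The documents print no SD and define the effect as the difference in mean change divided by the control-arm mean change. The standardised effect d was therefore back-solved from the printed power (two-sample t-test, noncentral t):

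| Outcome | Printed power (76 / 72 / 67 per arm) | Implied d | Value used |
|---|---|---|---|
| Sydney | .87 / .85 / .83 | .504 / .503 / .507 | .504 |
| CBI | .84 / .81 / .79 | .482 / .476 / .481 | .480 |

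Putting these back in at 72 per arm gives .852 (Sydney; printed .85) and .816 (CBI; printed .81). The printed power therefore matches one two-sided t-test of pre-to-post change at alpha .05.

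**2. Type I error with two time points.** Assume unit variances and a common correlation rho between all three visits. The two change scores share the baseline, so

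- covariance = rho − rho − rho + 1 = 1 − rho
- variance of each = 2(1 − rho)
- correlation = (1 − rho) / [2(1 − rho)] = .5, whatever rho is.

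For two two-sided 5% tests correlated at .5, the bivariate normal gives:

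- P(at least one significant) = .0907, about 9%
- P(both significant) = .05 + .05 − .0907 = .0093, about 1%.

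A null simulation (10,000 trials per rho, 60 per arm, complete normal data, rho .3 / .5 / .833) agrees: .051 / .052 / .050 for the post-treatment t-test alone, and .094 / .093 / .089 for a t-test at either time point.

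**3. Precision from the baseline score.** Per-arm variance, in units of the score variance:

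- change score: 2(1 − rho)
- baseline-adjusted: 1 − rho²
- ratio: (1 − rho²) / [2(1 − rho)] = (1 + rho)/2.

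At rho .5 the ratio is .75, so variance is 25% lower. At the pilot values (.833 and .839 under the tables) it is .917 and .920, about 8% lower.

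Power at the plan's 72 per arm, with change-score effect d/√[2(1 − rho)] and adjusted effect d/√(1 − rho²):

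| Outcome | rho | Effect, change | Effect, adjusted | Power, change | Power, adjusted |
|---|---|---|---|---|---|
| Sydney | .5 | .504 | .504/√.75 = .582 | .852 | .934 |
| CBI | .5 | .480 | .480/√.75 = .554 | .816 | .910 |

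At the pilot correlations all four powers exceed .998, so nothing material is gained.

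**4. What the mixed model would deliver.** Simulation of the three-visit model (6,000 trials, unstructured covariance, 72 per arm, rho .5, post-treatment contrast):

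| Outcome | Arms free at baseline | Arms equal at baseline | Baseline as covariate |
|---|---|---|---|
| Sydney | .841 | .933 | .932 |
| CBI | .811 | .909 | .908 |

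The first column is the change-score result and the other two are the adjusted result. The text of section 5.6 is compatible with any of the three.

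**The case against.** The strongest reply is that the mixed model is the principal analysis. Two sections name it, and the power section treats its t-test as a simple case of that model. The list of three model classes is general text, and Hypothesis 1 narrows it to linear mixed models for the Sydney. This stands against anyone who infers that no method is named. It does not supply a contrast or a visit. The power calculation rests on pre-to-post change, which points to the post-treatment visit, but Hypothesis 1 tests both visits and Hypothesis 2 claims benefit in both periods.

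A reader might also infer an error rate of 11% to 15%, by letting the t-test, the rank-sum test and a baseline-adjusted contrast each count at either visit. The documents do not support that. The choice between t-test and rank-sum is to be made as appropriate, not by which is significant, and no baseline-adjusted contrast is listed. Even 9% is conditional: the CBI hypothesis joins the two periods, and if both must succeed the error is about 1%. The plan states neither rule.

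Nor are the change-score tests invalid. Under randomisation they are unbiased and each keeps its 5% level. The precision argument carries weight only at the planning correlation, which the sponsor deliberately set below the pilot value; at the pilot values it has almost none. The three measured visits suggest that baseline is a response in the model, and if arms were held equal there the precision would already be secured.

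On covariates, the second rule refers back to the first, so the two thresholds are best read as a mismatch in wording.

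**Conclusion.** The point holds in a limited form. Mixed effects regression is named, but the decisive contrast, the decisive time point and the role of the baseline score are not, for either the Sydney or the CBI. The Type I error per primary outcome is about 9% if either time point may count and about 1% if both are required, against a nominal 5%. The first figure is a consequence of one permitted reading, not of a stated rule.

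Leaving baseline unadjusted costs up to 8 power points for the Sydney and 9 for the CBI at rho .5 and 72 per arm, and practically nothing at the pilot correlations. No size is attached to the covariate rules.

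The figures assume normal, complete and independent data, equal correlation among the three visits, and standardised effects back-solved from the printed power because no SD is given. The plan should be amended before data are analysed; nothing here shows that its tests are biased.

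**What to change.** For each of the Sydney and the CBI, write into section 5.6:

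1. One primary linear mixed model of the post-treatment and 6-month scores, with treatment, time, treatment-by-time, the baseline score, VISN (randomisation is within VISN) and a short fixed list of baseline covariates.
2. One time-point contrast from that model as the decisive test at two-sided 5%. Post-treatment would match the power calculation.
3. A statement that the change-score t-tests, the rank-sum tests and the other time point are supportive.
4. The fixed covariate list in place of both significance-test selection rules, with baseline comparisons kept as description only.

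The cost is SAP wording. The scores and VISN are already recorded, and no visit or procedure changes. What is given up is that the time point not chosen becomes supportive.
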